| TEST PRODUCT, DOSE, AND ROUTE OF ADMINISTRATION | 
Synvisc G-F 20 will be injected in the symptomatic knee using a standard supine lateral approach using a 20-gauge needle. Patients will be treated at baseline and followed out to three years. Patients may return for retreatment as early as 4 months post their prior injection if they meet the retreatment criteria pain levels for Worst Knee Pain. If the subjects need another injection, the follow-up cycle will restart at Visit 1 and the subject will be seen every 6 months and followed-up for 3 years.
 |
| CONTROL PRODUCT, DOSE AND ROUTE OF ADMINISTRATION | N/A |

| | |
|---|--|
| 
DURATION OF SUBJECT PARTICIPATION AND DURATION OF STUDY
 | 
Patients may return for retreatment as early as 4 months post their prior injection if they meet the retreatment criteria pain levels for Worst Knee Pain. If the subjects need another injection, the follow-up cycle will restart at Visit 1 and the subject will be seen every 6 months and followed-up for 3 years.
 
Approximate Time Requirements:
 
 • Baseline Screening: Informed Consent, Physical exam, patient questionnaire, injection, X-ray, walk test (Approx. 2 hours) and accelerometer test (3 days) • 6 months after injection: Physical exam, patient questionnaire, walk test (Approx. 1 hr) and accelerometer test (3 days) • 12 months after injection: Physical exam, patient questionnaire, walk test (Approx. 1 hr) and accelerometer test (3 days) • 18 months after injection: Physical exam, patient questionnaire, walk test (Approx. 1 hr) and accelerometer test (3 days) • 24 months after injection: Physical exam, patient questionnaire, walk test (Approx. 1 hr) and accelerometer test (3 days) • 30 months after injection: Physical exam, patient questionnaire, walk test (Approx. 1 hr) and accelerometer test (3 days) • 36 months after injection: Physical exam, patient questionnaire, walk test (Approx. 1 hr) and accelerometer test (3 days) • 15 min email or phone contact at 6, 12, and 18 weeks post each injection and clinic visit (total 4.5 hrs) 
Total time for the study will be approximately 8 clinical hours over 3 years, 21 days for the accelerometer test and 4.5 hrs of email/phone contact.
 |

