3 STUDY DESIGN

3.1 Study Overview

This study aims to study use of viscosupplementation as a treatment of pain for young individuals who are active. Typically viscosupplementation is considered an intervention for knee osteoarthritis often for older patients who are less active. Many young active patients can also develop knee osteoarthritis after trauma or surgery or for congenital reasons. Treatment of these patients commonly are steroid injections which have more biologically detrimental effects for cartilage compared to viscosupplementation Synvisc One injections which are a single injection will be used to determine effectiveness of reducing pain and maintaining an active healthy lifestyle for younger patients aged 30-50 years old.

This study will be an open label longitudinal cohort study with natural history over 3 years. Screening data will be reviewed to determine subject eligibility. Subjects who meet all inclusion criteria and none of the exclusion criteria will be entered into the study. Subjects enrolled in the cohort will have baseline functional testing performed including a motion gait analysis, 12 minute walk test, and 3-day accelerometer data. Subjects will receive a single 6 mL intra-articular injection of hylan G-F 20 in the target knee at baseline. All ongoing treatments will be monitored at 6 month intervals over the 3 year

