5.2 Inclusion Criteria

Inclusion Criteria:

1. Male or female patients aged 30-50 years
2. History of symptomatic unilateral primary or secondary knee OA for more than 6 months

3. Signed written informed consent
 4. Radiographic evidence of Kellgren-Lawrence Grade I or II OA of the target knee
 5. Body Mass Index (BMI) < 30 kg/m²
 6. Activity criteria (Tegner score > 3)
 7. Continued target knee OA pain despite conservative treatment \geq 3 months (e.g., weight reduction, physical therapy, analgesics)
 8. Willing to withhold intake of NSAIDs (including COX-2 inhibitors) and analgesics, for a washout period of minimum 3 days up to 21 days prior to baseline visit (depending on medication)
 9. Willing to discontinue prohibited treatments and medications throughout study period
- Baseline inclusion criteria
10. Completed OA medication washout period
 11. Target knee pain 4-8 (0-10 NRS) during most painful knee movement (Worst Knee Pain)
 12. If female, must have had a negative urine pregnancy test and used a medically acceptable form of contraception for at least 1 month prior to baseline and agree to continued use of contraception for the duration of the study. Otherwise, females must be surgically sterile, or postmenopausal (as documented in medical history) for at least 1 year. The fetal safety profile for G-F 20 is unknown. Pregnancy will affect the individual's regular activity levels. Females who become pregnant during the study will be excluded from the study. Subjects who become pregnant will be followed up by telephone every 3 months to check for any adverse effects. They will also be recommended to follow routine obstetric visits. Males should be able to father children as it has no expected effects on activity levels.

5.3 Exclusion Criteria:

1. Known allergy to hylan G-F 20 or any of its components, or to avian proteins, eggs, feathers, down, or poultry
2. Clinically apparent tense effusion or other acute inflammation of the target knee at baseline
3. History of target knee viscosupplementation treatment
4. History of major surgery for OA in target knee including arthroplasty or tibial osteotomy
5. Arthroscopic surgery or intra-articular steroid injection in target knee within six months of baseline visit
6. Significant (as judged by the Investigator) alignment deformity of target knee
7. Ipsilateral symptomatic OA of hip or ankle; contralateral symptomatic OA of hip, knee, or ankle
8. History of:
9. Septic OA of any joint

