10. Inflammatory arthropathy such as RA, gout, pseudogout, lupus, crystalline inflammatory arthropathy
11. Active infection of lower extremity
12. Known significant acute and/or concurrent medical disease including, but not limited to current malignancy, history of transplant surgery, congestive heart failure,

- significant unstable cardiovascular disease, renal hepatic pulmonary, endocrine, metabolic, or GI condition
13. Any known contraindication to acetaminophen
 14. Venous or lymphatic stasis in either leg
 15. Peripheral vascular disease
 16. Patient has been prescribed chronic opioid analgesics at time of baseline visit
 17. Concurrent multi-system or multi-limb trauma
 18. Patient plans to become pregnant during study period
 19. Patient plans to move significantly out of area, have surgery, or initiate or cease other OA treatments
 20. Knee pain improves during washout period
 21. Workman's Comp patient
 22. Written informed consent (and assent when applicable) obtained from subject or subject's legal representative and ability for subject to comply with the requirements of the study.
 23. Pregnant, breastfeeding, or unwilling to practice birth control during participation in the study.
 24. Presence of a condition or abnormality that in the opinion of the Investigator would compromise the safety of the patient or the quality of the data.

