8.1.12 Questionnaires and Assessments

Patients will either complete on their own or be asked questions from the WOMAC, Lysholm-Tegner, Worst Knee Pain, KOOS, and SF-12 assessments by their doctor or another study staff member who will record the appropriate scores during the screening visit. Patients will be assessed again with the Worst Knee Pain, KOOS, SF-12 and WOMAC assessments during their 6month, 18 month, 24 month, 30month, and 36month visits.

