 2. KOOS
 3. SF-12
 4. WOMAC

Email or phone contact at 6, 12 and 18 weeks post each injection and clinic visit to check for any changes in medical condition.

- Worst Knee Pain (0-10 NRS)
- Other treatment history
- Adverse events

| Office Visit | What you do |
|--|---|
| 1-3 weeks before starting study treatment | Physical exam X-ray Study questionnaire 12 minute walk test 3-day accelerometer test |
| Visit 1 - Baseline | Synvisc-One injection in the affected knee |

| | |
|--|---|
| 
Visit 2 – 6 months after injection Visit 3 – 1 year after injection Visit 4 – 1.5 years after injection Visit 5 – 2 years after injection Visit 6 – 2.5 years after injection
 
Email or phone contact at 6, 12 and 18 weeks after each injection and office visit
 | 
Physical exam Study questionnaire 12 minute walk test 3-day accelerometer test
 
Check up on your medical condition
 |
|--|---|

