APPENDIX 1. SCHEDULE OF STUDY VISITS

| | SCREENING | VISIT 1 | VISIT 2 6 months | VISIT 3 12 months | VISIT 4 18 months | VISIT 5 24 months | VISIT 6 30 months | VISIT 7 36 months |
|---|-----------|---------|---------------------|----------------------|----------------------|----------------------|----------------------|----------------------|
| Informed Consent | X | | | | | | | |
| Medical History | X | | | | | | | |
| Complete Physical Exam | x | | X | X | x | X | x | x |
| Abbreviated Physical Exam | | x | | | | | | |
| Height/weight | x | X | X | X | X | X | X | X |
| X-rays (flexion, weight bearing, lateral, and merchant views) | x | | | | | | | |
| Vital Signs | x | x | x | x | x | x | x | x |
| Motion Gait Analysis | X | | | | | | | |
| 12 Minute Walk Test | X | | X | X | X | X | X | X |
| 3-day Accelerometer Test | X | | X | X | X | X | X | X |
| Pregnancy Test | X | | | | | | | |
| Worst Knee Pain | X | | X | X | X | X | X | X |
| KOOS | X | | X | X | X | X | X | X |
| Lysholm-Tegner | X | | | | | | | |
| WOMAC | X | | X | X | X | X | X | X |
| SF-12 | X | | X | X | X | X | X | X |
| Dispensing or Administration of Study Drug | | X | | | | | | |
| Concomitant Medication Review | X | X | X | X | X | X | X | X |
| Adverse Experiences | | | X | X | X | X | X | X |

^a ±2 days

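### The schedule holds one Worst Knee Pain score before injection, at Screening, and none at Visit 1, so it does not support the entry rules that depend on washout

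*Combined protocol and SAP*

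**What the plan says.** Section 5.2 sets a washout "for a washout period of minimum 3 days up to 21 days prior to baseline visit (depending on medication". Under a sub-heading for baseline criteria it then requires that the washout is complete (item 10) and gives the pain range (item 11): "Target knee pain 4-8 (0-10 NRS) during most painful knee movement (Worst Knee Pain"). Section 5.3, item 20, excludes a patient if "Knee pain improves during washout period". It names no instrument and no amount of improvement.

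The scheduling text is as follows:

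- **Appendix 1**, which Section 8 presents as the required testing, has the row "Worst Knee Pain | X | | X". The columns are Screening, Visit 1, Visit 2, so the Visit 1 cell is empty. The injection is marked at Visit 1 only.
- **Section 8.1.12** has the questionnaires, including Worst Knee Pain, recorded at the screening visit, then says: "Patients will be assessed again with the Worst Knee Pain, KOOS, SF-12 and WOMAC assessments during their 6month" visit and at later ones.
- **Section 9** places Screening 1-3 weeks before treatment. Its Screening list omits Worst Knee Pain. Its office-visit table labels Visit 1 as Baseline and gives one activity: "Synvisc-One injection in the affected knee". The e-mail or phone scores at 6, 12 and 18 weeks all follow an injection or a clinic visit.
- **Section 3.1** says "Screening data will be reviewed to determine subject eligibility".
- **The synopsis**, under duration of participation, lists for baseline screening: "Informed Consent, Physical exam, patient questionnaire, injection, X-ray, walk test (Approx. 2 hours"). This puts questionnaire and injection under one heading.

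**The concern.** The baseline criteria imply an order: stop analgesics, complete the washout, score the knee, then inject. Exclusion 20 adds a comparison between the start and end of washout. The schedule provides one score, and a single score cannot serve both rules.

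Two things depend on this. First, the study has one arm, and Section 13 tests the proportion with Worst Knee Pain ≤ 3 against a fixed 50%. Who enters therefore bears directly on the result. A patient already at ≤ 3 on the injection day needs only to stay there to count as a responder, while a patient above 8 has further to fall. Second, change in Worst Knee Pain over 36 months is a secondary endpoint (Section 4.2). If the only pre-injection score precedes washout, the effect of stopping analgesics cannot be separated afterwards from the effect of the injection.

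**Working it through.** **1. What each rule needs and what is scheduled**

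| Rule | Needs | Scheduled before injection |
|---|---|---|
| 5.2 items 10-11 | one score after washout | one score, at Screening |
| 5.3 item 20 | a comparison across washout (two scores, if scored) | one score, at Screening |

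**2. Timing.** Inputs: Screening on day -21 to day -7 (Section 9); washout of 3 to 21 days, read as running up to the baseline visit (5.2 item 8); Visit 1 on day 0 (Section 9 table). In whole days this gives 15 × 19 = 285 combinations. For Screening d days before injection, the score falls at or before the start of washout when the length is 3 to d days, which is d - 2 lengths. Summing over d = 7 to 21: 5 + 6 + … + 19 = 180. In the other 285 - 180 = 105 the score falls during washout. In none does it fall after washout ends.

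**3. Possible readings**

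- *Screening before washout.* Section 8 requires consent before any study activity and Appendix 1 places consent at Screening, so a study-required washout should start afterwards. A 21-day washout then fits only if Screening is the full three weeks before injection. The 4-8 range is applied before washout is complete.
- *Screening after washout, or on the injection day (synopsis line).* The score is post-washout, so the 4-8 range is supported. Exclusion 20 has no earlier score. The same-day version also conflicts with Section 9 and Appendix 1 and puts a required washout before consent.

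Each reading yields one score and leaves at least one rule unsupported.

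**4. Illustrative size, on assumed inputs.** The documents give no score distribution. Assume Screening and Visit 1 scores are bivariate normal, rounded and clipped to 0-10, with mean 5.5 or 6.5, SD 1.5 or 2 and retest correlation 0.6 or 0.9. Washout either leaves mean pain unchanged or raises it by 1 point. That is 8 settings per shift, with 1,000,000 draws each, conditioned on Screening 4-8.

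| At Visit 1 | No shift | +1 point |
|---|---|---|
| ≤ 3 | 1-11% | 0-4% |
| above 8 | 1-11% | 8-26% |
| outside 4-8 | 4-17% | 8-27% |
| mean Visit 1 minus Screening | -0.13 to +0.11 | +0.86 to +1.07 |

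**5. Effect on the primary test if no one checked pain at baseline.** The Wilson 95% lower limit exceeds 0.50 from 71/120 or 88/150. The exact tails at a true rate of 0.50 are 0.0274 and 0.0204. Let the true rate be 0.50 in eligible patients, rL = 0.5, 0.7 or 0.9 in those at ≤ 3, and rH = 0.3, 0.4 or 0.5 in those above 8:

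π = 0.50·P(4-8) + rL·P(≤ 3) + rH·P(> 8)

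Over 72 combinations per shift, the chance of declaring non-inferiority at n = 120 is 0.8-17.1% with no shift and 0.1-5.5% with +1, against 2.7% if all are eligible. It exceeds 2.7% in 40 of 72 and 16 of 72 combinations respectively. The effect can go either way.

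**6. Cost of the check.** Screening passers needed to inject 150 = 150 / (1 - share failing at Visit 1). For the 4-8 range alone: 150 / (1 - 0.043) = 157 to 150 / (1 - 0.271) = 206. Adding exclusion for a fall of at least 2 points gives 160-222; at least 1 point gives 167-283. With no shift, 22-31% fall by 1 point or more while staying within 4-8, from retest variation alone. For a 2-point fall the share is about 1.5-13%.

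**The case against.** The strongest reply is that eligibility is governed by Section 5.2, not by a tick in a table. The 4-8 range is a baseline criterion, Visit 1 is labelled Baseline, and exclusions 2 and 16 are also judged at baseline. Injecting a patient outside the range would be a protocol violation under Section 12. Exclusion 20 can be judged from history. The Section 9 lists are plainly incomplete: they omit Visit 1 vital signs and medication review, which Appendix 1 marks. The case report forms in Appendix II might record a Visit 1 score.

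Much of this stands. A careful site can apply the rules with an unscheduled question, and the Section 9 omissions alone would prove little. But Appendix 1 and Section 8.1.12 agree on the gap, Section 3.1 ties eligibility to Screening data, and nothing in the available text provides for recording a Visit 1 score. If the forms do record one, only the schedule text needs correcting.

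A reader might infer that patients already at ≤ 3 will be injected and that the trial is tilted toward success. The documents do not support that. The calculation in step 5 assumes no baseline check at all, every input to it is assumed, and the sign changes across plausible values. The gap alters no stated sample-size or power figure.

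A reader might also infer that the Visit 1 score is the only proper baseline for change. That is debatable. Section 6.1 allows oral medication during follow-up and no washout before follow-up visits is scheduled, so an off-medication baseline could credit resumed analgesics to the injection.

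**Conclusion.** The point holds as a mismatch between the schedule and the entry rules. One Worst Knee Pain score is scheduled before injection, at Screening, and none at Visit 1. With Screening as a separate earlier visit, which is what Section 9 and Appendix 1 describe, no post-washout score is scheduled for the 4-8 range. On the synopsis's same-day reading, only exclusion 20 is left without the earlier score it needs. In either case, improvement during washout is undefined.

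It is not evidence that ineligible patients will enter, and the direction and size of any effect on the responder rate are not established. The 4-27% outside 4-8 at Visit 1 is a conditional illustration that rests on the assumed means, SDs, correlations and washout shift. The change endpoint would differ by up to about 1 point according to which score is the baseline, if washout raises pain by 1 point. The correction is worth making because a score not taken before injection cannot be recovered later.

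**What to change.** - Mark Worst Knee Pain at Visit 1, after washout and before injection, in Appendix 1 and Sections 8.1.12 and 9 (including the office-visit table). List it at Screening in Section 9.
- Apply inclusion criterion 11 to the Visit 1 score.
- Apply exclusion 20 to the change from Screening to Visit 1, with a stated threshold that allows for retest variation, for example a fall of at least 2 points. State that Screening precedes washout.
- Correct the synopsis time list so that the injection is at Visit 1.
- Report Worst Knee Pain change from both Screening and Visit 1.

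The direct cost is one 0-10 question at a visit that already takes place. The downside is extra failures at Visit 1: 157-206 Screening passers for 150 injected under the assumed distributions, or 160-222 with a 2-point rule. These count patients who have already passed Screening; counting everyone screened, the 4-8 rule alone needs about 177-266. Failures on the range are patients the protocol already means to exclude. The improvement rule will also remove some whose pain has not truly changed, which is the reason to avoid a 1-point threshold.

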6 CONCURRENT MEDICATIONS

All subjects should be maintained on the same medications throughout the entire study period, as medically feasible, with no introduction of new chronic therapies. Patients can receive any other conservative treatments (e.g., oral medications, physical or other therapy, acupuncture, etc., except other injection treatments) and current treatments will be documented during each patient encounter.

6.1 Allowed Medications and Treatments

Patients can receive any other conservative treatments (e.g., oral medications, physical or other therapy, acupuncture, etc., except other injection treatments) and current treatments will be documented during each patient encounter.

7 STUDY TREATMENTS

7.1 Method of Assigning Subjects to Treatment Groups

All subjects in this study will receive the treatment.

7.2 Blinding

Since there is no randomization in this study, blinding will not be necessary,

7.3 Formulation of Test and Control Products

There will be no control products in this study.

7.3.1 Formulation of Test Product

The test product, Synvisc-One, has a unique composition. Synvisc-One, like SYNVISC® , is a mixture of two hylan polymers derived from American and Canadian chicken comb hyaluronan. Hylans are produced by chemically cross-linking hyaluronan in two steps (shown in figure). Synvisc-One is hylan G-F 20, meaning it is 80% hylan A fluid plus 20% hylan B gel. This composition yields a molecular weight and viscoelastic properties that closely match healthy synovial fluid.

Synvisc-One™ (hylan G-F 20) is an elastoviscous high molecular weight fluid containing hylan A and hylan B polymers produced from chicken combs. Hylans are derivatives of hyaluronan (sodium hyaluronate). Hylan G-F 20 is unique in that the hyaluronan is chemically cross-linked. Hyaluronan is a long-chain polymer containing repeating disaccharide units of Na-glucuronate- N-acetylglucosamine

Hylan polymers (hylan A + hylan B) 16 mg
Sodium chloride 17 mg
Disodium hydrogen phosphate 0.32 mg
Sodium dihydrogen phosphate monohydrate 0.08 mg
Water for injection q.s. to 2.0 mL

SYNVISC® (hylan G-F 20) and Synvisc-One® (hylan G-F 20) are indicated for the treatment of pain in osteoarthritis (OA) of the knee in patients who have failed to respond adequately to conservative non pharmacologic therapy and simple analgesics, e.g., acetaminophen.

7.3.2 Formulation of Control Product

There will be no control or placebo product in this study.

7.3.3 Packaging and Labeling

The package insert is attached. Synvisc-one is supplied in single use boxes that will contain the statement, “CAUTION-Investigational device Limited by Federal law to investigational use.” The boxes will be labeled and shipped with this investigational packing to the UCSF Investigational Pharmacy.

7.4.1 Dosage/Dosage Regimen

Subjects will receive a single 6 mL intra-articular injection of hylan G-F 20 in the target knee at baseline. Patients can receive any other conservative treatments (e.g., oral medications, physical or other therapy, acupuncture, etc., except other injection treatments) and current treatments will be documented during each patient encounter. An initial injection of hylan G-F 20 will be injected in the symptomatic knee using a standard supine lateral approach using a 20 gauge needle. A face to face follow up visit will be carried out 6 months after first injection with additional face to face meetings every 6 months thereafter unless the subject requires an additional injection of hylan G-F 20. Hylan G-F 20 treatments can be administered up to three times each year during the study duration. After each injection, follow up measures will be carried out using secure e-mail or phone contact at 6 weeks, 12 weeks, 18 weeks after each in-office evaluation or injection. Follow up will consist of WOMAC, Lysholm score, and Tegner score. . Patients may return for retreatment of hylan G-F 20 if symptoms recur after at least 4 months following their previous injection and they meet the inclusion criteria for pain levels on the following WOMAC questions A1 (How much pain have you had walking on a flat surface?), C8 (How much difficulty have you had going down the stairs?), C9 (How much difficulty have you had when going up the stairs?), C10 (How much difficulty have you had when getting up from a sitting position?) and/or C23 (How much difficulty have you had while doing heavy household chores?). Inclusion criteria for pain level is defined by selecting moderate, severe, or extreme on all questions A1, C8, C9, C10 and/or C23. Those subjects who select mild or no pain levels on any of A1, C8, C9, C10 and/or C23, will not meet the criteria for WOMAC pain level and retreatment. Patients requiring three injections of hylan G-F 20 in 4 months or less will be allowed to exit the cohort after their six-month follow up following the third injection. Otherwise, patients will be followed until they reach the 3 year follow up, or drop out for other injection treatments or surgical treatment. Therefore, patients would potentially be able to receive up to 9 injections during the 3 year study.

